- 7. **PFTs** with volumes, spirometry, DLCO and room air pulse oximetry. Patients will be required to obtain a pulmonary function test, despite the exclusion of bleomycin. The DLCO adjusted for hemoglobin must be greater than 70% predicted to enter the study and to continue with brentuximab vedotin.

- 8. **Bone marrow biopsy** for histology and determination of percent bone marrow involvement. If bone marrow involvement by lymphoma has already been documented after bone marrow biopsy performed more than 6 weeks prior to registration, the biopsy does not have to be repeated.
- 9. Central pathology review for confirmation of histology of lymphoma specimen: Biopsy material at diagnosis will be sent to confirm HL and histologic subtype. (See Appendix 20.1 and 20.7 for the acceptable specimens required for central review and for handling instructions).

All specimens will be reviewed by a panel of pathologists and must be submitted within 30 days of study enrollment. Patients who are found not to have HIV-HL will be withdrawn from the study

- 10. Laboratory tests, including:
 - CBC with differential and sedimentation rate (within 2 weeks prior to patient registration).
 - Serum chemistries: electrolytes (Na, K, Cl, bicarbonate, Ca, Mg, and phosphorus), glucose, blood urea nitrogen (BUN), creatinine, total bilirubin, alkaline phosphatase (ALP), LDH, total protein, albumin, AST and ALT (within 2 weeks prior to patient registration).
 - CD4 and CD8 cell count.
 - HIV-1 RNA viral load assessed by any approved viral load assay at the local laboratory. This must be performed within 21 days prior to Cycle 1, Day 1. (The HIV viral load assay must detect at minimum viremia >200 copies/mL to be consistent with the DHHS HIV treatment guidelines).
 - Assessment for Hepatitis C antibody, Hepatitis B core antibody, Hepatitis B surface antigen (HBsAg), and Hepatitis B surface antibody.
 - Serum pregnancy test for women of childbearing potential (within 7 days prior to Cycle 1 chemotherapy). (See Section 13.1.1 under pregnancy and breastfeeding for guidelines on the use of pregnancy category D medications, which includes brentuximab vedotin and dacarbazine.)
- 11. Blood collection for biological analyses (cf. Appendix 20.7) after signature of informed consents for biological and genetic studies.

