9.4 Evaluation during treatment

- 1. Update **medical history** prior to each cycle of chemotherapy. History to include concomitant medication changes and any signs and symptoms. Reportable adverse events must be recorded in AdvantageEDC. To be performed within 48 hours prior to or on first day of each cycle.
- 2. **Physical examination** prior to each cycle of chemotherapy. Examination to include performance status (Appendix 20.5). All subjects will be evaluated for clinical response by physical examination prior to receiving treatment on each cycle. The exam should occur within 2 days prior to the start of each cycle but may occur on Day 1 of cycle. Disease measurable by physical examination will be recorded in two dimensions if possible. To be performed within 48 hours prior to or on first day of each cycle.
- 3. **FDG-PET/CT**. Combined FDG-PET/CT or FDG-PET + CT scans with and without IV contrast are required for this study. If a patient has an allergy to IV contrast, a CT scan without contrast will be permitted.
 - Restaging evaluation by a full body FDG-PET/CT within Day 22-28 of Cycle 2 (i.e., 7-13 days after the Cycle 2 Day 15 doses of AVD-BV). If the CT portion of the PET/CT is a non-contrast CT, an additional CT scan with and without contrast must be obtained. Tumor measurements and SUVs must be

documented. A neck CT must be included if palpable neck nodes were present at baseline and a diagnostic CT is being performed.

- As the false positive rate of FDG-PET scans may be higher in the HIV population, a biopsy of an unexpected FDG-PET avid lesion is recommended but remains at the discretion of the investigator.
- 4. **PFT** with volumes, spirometry, DLCLO, and room air pulse oximetry will be performed after every 2 cycles, on day 1 of cycles 3 and 5, within 7 days of cycle initiation. The DLCO adjusted for hemoglobin must be greater than 70% predicted to continue with therapy.
- 5. Neuropathy evaluation by completing the FACT/GOG-neurotoxicity **questionnaire** at the beginning of each cycle. To be performed once within 48 hours prior to or on first day of each cycle (Appendix 20.6).
- 6. **CBC** with differential within 48 hours of day 1 and 15 of each cycle. Results of CBC must be known prior to treatment.

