9.5 Follow-up assessments

The studies listed below will be repeated post-therapy within 6-8 weeks of the last treatment dose (6-8 weeks after Cycle 6 Day 15) and then every 3 months (+/- 7 days) thereafter for 2 years; every 6 months (+/- 7 days) for the third through the fifth years unless otherwise specified. All study subjects should be followed for up to 5 years after treatment discontinuation or until death if occurring before 5 years of treatment discontinuation. Patients who discontinue all protocol therapy after a CR or PR are followed for up to 5 years after treatment for recurrence and survival. Patients who discontinue protocol therapy due to disease progression or other reasons are followed for survival for up to 5 years after treatment discontinuation. No additional studies except follow up for survival are required after disease progression. In those instances in which a third party payer denies payment for some or all of these laboratory analyses, absence of these test results will not be considered a protocol violation.

- 1. Medical history.
- 2. Physical examination, including performance status (see Appendix 20.5,

Performance Status Scale), vital signs (weight, height, body surface area), neurological examination, and if possible, two dimensional measurement of all palpable, peripheral lymph nodes and measurement of other sites of disease present on physical exam.

- 3. At the conclusion of chemotherapy, a full body FDG-PET/CT scan will be done between 6-8 weeks post the final treatment dose, Cycle 6 Day 15. This will be the final FDG-PET/CT needed for the study. A combined FDG-PET/CT or FDG-PET + CT scans with and without IV contrast are required for the post- treatment scan. If a patient has an allergy to IV contrast, a CT scan without contrast will be permitted. As the false positive rate of FDG-PET scans may be higher in the HIV population, a biopsy of an unexpected FDG-PET avid lesion is recommended but remains at the discretion of the investigator.
- 4. **CT scan** with oral/IV contrast every 6 months for 5 years. To begin 6 months from the post treatment FDG- PET/CT scan, obtained 6-8 weeks post the final chemotherapy dose (See Section 9.5).
- 5. **PFT** with volumes, spirometry, DLCO and pulse oximetry for any patient with a DLCO corrected for hemoglobin \leq 70% during therapy. To be repeated at all post-treatment evaluations until normalization.

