9.6 Early Discontinuation of Therapy

Subjects discontinuing therapy early (i.e., PD or stable disease, administrative reasons, subject non- compliance, etc.) will have a medical history update and complete physical examination. The examination will include performance status and blood drawn for the following studies within 1 month after treatment discontinuation, unless otherwise noted. See Section 12 for a list of reasons for study termination. Subjects will be followed for survival only for 5 years after the last date of treatment:

- **CBC** with differential.
- Serum chemistries: electrolytes (Na, K, Cl, bicarbonate, Ca, Mg, and phosphorus), glucose, blood urea nitrogen (BUN), creatinine, total bilirubin, alkaline phosphatase (ALP), LDH, total protein, albumin, AST and ALT.
- **CD4 and CD8 cell** count (do not repeat if done within 1 month from removal from treatment).
- **HIV-1 RNA viral load** to be evaluated at the local laboratory, do not repeat if done within 1 month from removal from treatment).

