10.6.1.4 Dose Modifications for Pulmonary Toxicity

Pulmonary toxicity will be defined by grade 3 or 4 dyspnea, pneumonitis, and/or hypoxia that persists for at least three days. There must be no evidence of other etiologies, including left atrial hypertension, congestive heart failure, infection, metabolic abnormalities, or cancer related causes (e.g., malignant pericarditis).

Patients who develop pulmonary toxicity associated with brentuximab vedotin may benefit from treatment with corticosteroids. However, there are no published guidelines to suggest the most appropriate dosing or duration of treatment. Administration of 100 mg of oral or intravenous prednisolone in single daily or two divided doses has been reported to improve symptoms in adults with pulmonary toxicity secondary to gemcitabine. The suggested dose for patients who develop pulmonary toxicity is methylprednisolone 1 mg/kg IV every 12 hours for a minimum of seven days. Patients who develop pulmonary toxicity meeting the above definition will be taken off protocol therapy.

See Section 13.1 for a complete listing of potential adverse events and Section 13.1.1 for special precautions and safety issues.

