Impaired Hepatic Function	All patients with direct bilirubin ≤ 2 x the upper limit of normal (ULN) will receive a full initial dose of doxorubicin and vinblastine. If the direct bilirubin rises to ≥ 2 x ULN (but ≤ 5 x ULN), the doxorubicin and vinblastine doses must be reduced by 50% of last dose received to avoid undue hepatic toxicity. Full doses should be given once the direct bilirubin is ≤ 2 x ULN. If the direct bilirubin rises to ≥ 5 x ULN, doxorubicin and vinblastine should be discontinued for that cycle. If the direct bilirubin has not recovered to ≤ 2 x ULN by the time the next cycle is due, then remove patient from protocol treatment. In cases of obstruction of the biliary duct by a tumor mass, a biliary drainage stent should be placed prior to chemotherapy. Values must be within protocol eligibility at treatment initiation. Direct Bilirubin with appropriate Doxorubicin and Vinblastine Dose Adjustments ≤ 2 x ULN = 100% of last dose received
	> 2 - 5 x ULN = 50% of last dose received
	> 5 x ULN = discontinue (i.e., do not administer)
Neuropathy	Once brentuximab vedotin has been discontinued, patients experiencing Grade 3 vinblastine-neuropathy (e.g., obstipation, weakness) will have the dose of vinblastine reduced by 50% for all further cycles of AVD. Patients experiencing Grade 4 vinblastine neuropathy will have this drug omitted from all future cycles of AVD.
Pulmonary Toxicity	Every 2 cycles PFT will be performed. The DLCO adjusted for hemoglobin must be greater than 70% to continue with brentuximab vedotin.
Weight	If a subject's weight has changed more than 10% from baseline or the prior dose, the new BSA must be used on the next cycle. For a weight change of 10% or less, doses may be adjusted according to the BSA or remain the same in conjunction with institutional guidelines.

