13.0 CRITERIA FOR PREMATURE DISCONTINUATION OF THE STUDY

13.1 Premature withdrawal from trial intervention

After enrollment, subjects will be permanently withdrawn from study treatment for any of the following reasons. In the event of withdrawal from treatment, the reason for study treatment removal and the date the subject was removed must be documented in the Off Protocol Treatment Form in AdvantageEDCSM. See Section 9.6 on evaluations to be performed at early discontinuation of therapy.

- 1. Participants who experience a delay of over 7 days in cycle 1 will be removed from the study. For subsequent cycles, if two sequential doses of AVD + BV or AVD alone are held due to unresolved toxicity, leading to a treatment delay of an additional 2 weeks (i.e., 4 weeks between doses), the participant will be taken off protocol therapy. The participant will be followed for survival and may resume AVD treatment off study.
- 2. Severe toxicities as outlined in Section 10.6.1.
- 3. Progressive lymphoma at any time while on study.
- 4. Voluntary withdrawal.
- 5. The investigator has the right to remove subjects from study for clinical reasons which he or she believes to be life threatening or resulting in significant morbidity to the subject.
- 6. Any subject who develops HBV reactivation or acute Hepatitis B as defined by the reappearance of a previously suppressed hepatitis B surface antigen, a positive IgM hepatitis B core antibody, and a positive viral load. Any patient with Hepatitis B or C who has worsening liver function as defined by Section 10.6.2 will also be removed from study.
- 7. Any subject who on repeat PFT is found to have a DLCO when corrected for anemia less than 70%.
- 8. Subjects who become pregnant or breast-feed.
- 9. Subjects with progressive disease at the end of cycle 2 will be removed from study treatment, while patients with stable disease may be removed from the study treatment at the discretion of the local responsible investigator. Progressive or stable disease defined at cycle 2 will be based by CT criteria only, as FDG-PET has yet to be validated in HIV-associated HL.
- 10. If found by central pathology review to not have the diagnosis of HL.

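### Some sections put participants who stop therapy early on survival-only follow-up even without progression, so progression may go unseen for the pooled two-year PFS

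*Combined protocol and SAP*

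**What the plan says.** **Follow-up after early stopping.** French 9.6 covers early discontinuation. Its examples are progression, stable disease, administrative reasons and non-compliance, and the list is left open. It asks for history, examination, blood count, chemistries, CD4/CD8 and viral load, and then says: "Subjects will be followed for survival only for 5 years after the last date of treatment". AMC 8.4.1 has the matching sentence. The French synopsis and AMC 4.5 apply survival-only follow-up to stops for progression or for other reasons, directly after a sentence that gives responders recurrence follow-up.

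French 9.5, matched by AMC 8.3, says: "Patients who discontinue all protocol therapy after a CR or PR are followed for up to 5 years after treatment for recurrence and survival". Its next sentence gives those who stop for progression or other reasons follow-up for survival, without the word *only*. It then limits studies to survival follow-up once the disease has progressed. The final PET/CT is timed 6-8 weeks after cycle 6 day 15, and CT follows every six months from that scan.

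**The DLCO rule (French protocol only).** Lung function is repeated at day 1 of cycles 3 and 5. Section 10.6.2 says: "The DLCO adjusted for hemoglobin must be greater than 70% to continue with brentuximab vedotin". Sections 8.1 (item 17) and 9.3 also tie the condition to brentuximab vedotin. Section 9.4 says: "The DLCO adjusted for hemoglobin must be greater than 70% predicted to continue with therapy". Section 13.1 opens with "subjects will be permanently withdrawn from study treatment for any of the following reasons", and its item 7 reads "Any subject who on repeat PFT is found to have a DLCO when corrected for anemia less than 70" per cent. Section 13.1 refers its whole list to 9.6 for the evaluations at early discontinuation.

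**The concern.** Two-year PFS is the primary endpoint, estimated by Kaplan-Meier on pooled French and US data (French 16.0 and 16.2). Survival contacts record deaths, but without scheduled scans progression may be found late or not at all. If a participant stops for toxicity or another reason while free of progression, and the site follows 9.6, the PFS curve loses that participant's progression information from then on. Another site may follow 9.5 and keep scanning. Ascertainment would then depend on which section was read, and perhaps on the reason for stopping. Neither French 16.2 nor AMC 11.2 states a censoring rule, so how such a participant counts is also open.

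**Working it through.** **1. The follow-up sentences side by side, for a participant who stops early without progression**

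| Place | CR or PR at stopping | Stable disease at stopping |
|---|---|---|
| French 9.5, AMC 8.3 | recurrence and survival; the other-reasons sentence adds survival, so both can be met | survival sentence only, yet studies are reduced only after progression |
| French synopsis, AMC 4.5 | recurrence sentence and survival-only sentence both fit | survival sentences only |
| French 9.6, AMC 8.4.1 | survival only; no imaging listed | survival only; stable disease is named; no imaging listed |

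For a responder, the sentences within 9.5 can be reconciled. The conflict lies in the word *only* in the synopsis and 9.6 (and their AMC counterparts). For stable disease no section has a recurrence sentence.

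**2. Scans lost on the survival-only reading.** Assume that the PFS clock starts at cycle 1 day 1 and that there are no delays.
- Cycle 3 day 1 is day 56 (week 8), leaving 96/104 weeks = 92%. Cycle 5 day 1 is day 112 (week 16), leaving 88/104 = 85%.
- The only on-treatment scan is at cycle 2 day 22-28.
- Full course, last dose in week 22: PET/CT in weeks 28-30 and CT in weeks 54-56 and 80-82. The next CT, in weeks 106-108, falls outside. That is 3 scans.
- Survival only: 0 scans.
- Scans kept and timed from the last dose: a last dose in week 6 gives PET/CT in weeks 12-14 and CT in weeks 38-40, 64-66 and 90-92. A last dose in week 14 gives PET/CT in weeks 20-22 and CT in weeks 46-48, 72-74 and 98-100. That is 4 scans in either case.

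**3. The plan's own precision.** French 16.2 and AMC 11.2 give 51 participants, PFS of 85% and a 95% interval of ±10 points. The Wald formula gives n = 1.96² × 0.85 × 0.15 / 0.10² = 48.98, so 49; the stated 51 is slightly more. At n = 51 the half-width is 1.96 × √(0.85 × 0.15 / 51) = 1.96 × 0.05 = 9.8 points.

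**4. Shift in the estimate.** Suppose k participants are censored at stopping, before the others' events, and have true two-year PFS p, while the rest have 85%. Kaplan-Meier then estimates about 85%, and the true cohort value is [(51 − k) × 0.85 + k × p]/51. The shift is k × (0.85 − p)/51.

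| p | k = 1 | k = 2 | k = 3 |
|---|---|---|---|
| 0 | +1.67 | +3.33 | +5.00 |
| 0.50 | +0.69 | +1.37 | +2.06 |
| 0.70 | +0.29 | +0.59 | +0.88 |
| 0.85 | 0 | 0 | 0 |
| 1 | −0.29 | −0.59 | −0.88 |

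A Kaplan-Meier simulation with censoring at week 8 or 16 (4,000 runs, k = 1) agrees to within 0.06 point. The single-participant extreme of 1.67 is 1.67/9.8 = 0.17 of the half-width.

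**5. Precision.** If k participants contribute nothing, the half-width at n = 51 − k is 9.90 (k = 1), 10.00 (k = 2), 10.10 (k = 3) and 10.32 (k = 5).

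**The case against.** **The text already keeps low-DLCO participants in the schedule.** French 9.5 item 5 orders repeat lung function at all post-treatment evaluations for anyone whose DLCO fell to 70% or below. The flow chart (21.2) appears to place this at the end-of-treatment visit, where the final PET/CT also sits. This stands: it implies attendance, so a reader should not infer that a DLCO stop certainly ends imaging. It does not settle the matter. The entries order lung function, not scans, and can be read as adverse-event follow-up under the synopsis. The flow chart's early-discontinuation column appears to carry no scan.

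**The specific responder sentence governs, and other reasons is residual.** This is a fair reading of 9.5, and it stands there. It does not remove *only* from 9.6 or the synopsis, and it offers nothing for stable disease.

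**If a low DLCO stops brentuximab vedotin alone, AVD and its scans continue.** This is correct for that participant. A reader might infer instead that a low DLCO must stop all protocol therapy, given 13.1 and 10.6.1.4 ("Patients who develop pulmonary toxicity meeting the above definition will be taken off protocol therapy"). The documents do not settle this. Sections 8.1, 9.3 and 10.6.2 name brentuximab vedotin only. The AMC counterpart to 10.6.1.4 (5.1.2) adds brentuximab vedotin in parentheses after protocol therapy. AVD alone is allowed elsewhere in the dose-modification rules. The follow-up gap does not depend on the answer, because it covers every early stopper.

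**The effect is minor.** This stands. The figures for p = 0.50 and 0.70 are also upper bounds where some failures are deaths, since survival follow-up would record those.

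**Conclusion.** The concern holds as a conflict between follow-up rules in both protocols. French 9.6 and the synopsis, with AMC 8.4.1 and 4.5, can put a non-progressing early stopper on survival-only follow-up. French 9.5 and AMC 8.3 reserve that reduction for after progression. The French DLCO withdrawal is one example among several.

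The effect on the primary estimate is probably small: about −0.3 to +1.7 points per participant, against a half-width of 9.8. This assumes censoring at stopping, 85% PFS in everyone else and a clock from cycle 1 day 1. The number affected is not in the documents. DLCO stops are limited to the 20 planned French participants; other early stops can come from all 51. A reader might infer that two-year PFS will be materially overstated or the ±10 target missed. The documents do not support that. Nothing in them links low DLCO to progression, the shift is zero if early stoppers do as well as the rest, and the target is missed only from three participants with no information, a count that is itself assumed.

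**What to change.** In French 9.5, 9.6 and the synopsis, and in AMC 4.5, 8.3 and 8.4.1, state that anyone who stops protocol therapy without progression, for any reason, keeps the post-treatment PET/CT (timed from the last dose) and the six-monthly CT until progression, and that survival-only follow-up starts at progression. Timing from the last dose is needed because the present schedule counts from cycle 6 day 15.

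The cost is a French amendment and a matching AMC change. Each participant stopped at cycle 3 or 5 day 1 would have about one PET/CT and three CTs within two years. All are scan types already in the schedule, though some fall at visits that survival-only follow-up would not have included.

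Separately, as wording clean-up, use one DLCO cut-off. The present versions (above 70% to continue; 70% or below in 9.5; below 70% in 13.1 and the flow chart) differ only at exactly 70%. Say also whether a low DLCO stops brentuximab vedotin alone or all protocol therapy. That is a clinical decision for the sponsor, and this point does not recommend stopping AVD.

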10.7 Drug Dispensation and accountability

10.7.1 Responsibilities

All drug packages are to be inspected upon receipt at the study site prior to being drawn up. If any particulate matter is detected, the packaging is not to be used. Damaged packaging is to be reported to the sponsor and stored until instructions have been given.

The Investigator, the Hospital Pharmacist, or other personnel allowed to store and dispense Investigational Product (SGN-35 / Brentuximab Vedotin) are responsible for ensuring that the Investigational Products used in the clinical trial are securely maintained as specified by the Sponsor and in accordance with the applicable regulatory requirements. All Investigational Medical Products are stored in accordance with labelling and shall be dispensed in accordance with the Investigator's prescription. The Investigator is in charge of ensuring that an accurate record of Investigational Product issued and returned is maintained. Any quality issue noticed with the receipt or use of an Investigational Product (deficient IP in condition, appearance, pertaining documentation, labelling, expiry date, etc.) should be promptly notified to the Sponsor, who will initiate a complaint procedure. Under no circumstances will the Investigator supply Investigational Product to a third party, allow the Investigational Product to be used other than as directed by this Clinical Trial Protocol, or dispose of Investigational Product in any other manner.

The responsible investigator at each participating institution must be registered with CTEP, DCTD through an annual submission of FDA form 1572 (Statement of Investigator), Curriculum Vitae, Supplemental Investigator Data Form (IDF),
and Financial Disclosure Form (FDF). If there are several participating investigators at one institution, CTEP supplied investigational agents for the study should be ordered under the name of one principal investigator at that institution.

